5.6.2 Handling of withdrawals

[figure not shown]
All participants withdrawn will ideally complete all study visits including Day 30 follow-up if able, as per routine clinical practice. Withdrawn patients will be included in an intention to treat analysis.

5.6.3 Study Closure

Participants will be informed of study closure and will continue follow up as per routine clinical practice post transplantation.

6 STUDY VISITS AND PROCEDURES SCHEDULE

Study Flow Chart

Timeline for follow up wound assessments:

Day 7 – The dressing is taken down for review and not replaced unless indicated. The review will include a microbiology swab (MCS); photo of the wound; modified ASEPSIS wound assessment; a pain assessment (NRS) and patient quality of life questionnaire (EQ-5D).

Day 14 – The dressing is taken down for review and not replaced unless indicated. The review will include a microbiology swab (MCS); photo of the wound; modified ASEPSIS wound assessment; a pain assessment (NRS) and the quality of life questionnaire (EQ-5D).

Day 30 (+/- 3 days) – The patient will present for follow up for an extended wound review by a study clinician or wound CNC, and a vascular sonographer. The review will include a modified ASEPSIS wound assessment; a photo of the wound; a pain and scar assessment (POSAS); a quality of life questionnaire (EQ-5D) and an ultrasound of the transplanted kidney which will also identify deep wound complications.

Day 90 (+/- 3 days) – The patient will present for follow up for wound review and ultrasound, which will include a photo of the wound; a scar assessment (POSAS); a quality of life questionnaire (EQ-5D) and an ultrasound of the transplanted kidney which will also identify deep wound complications.

Event	Day 0 Enrolment	Day 7	Day 14	Day 30 (+/- 3 days)	Day 90 (+/- 3 days)
Screening for Inclusion / Exclusion criteria	✓				
Participant Information Sheet and Consent Form (PISCF)	✓				
Routine perioperative data collection (Appendix C)	✓	✓	✓	✓	✓
Modified ASEPSIS wound assessment (Appendix B)		✓	✓	✓	✓
Photo of wound using REDCap App		✓	✓	✓	✓
Quality of life questionnaire (EQ-5D-5L) (Appendix D)		✓	✓	✓	✓
Microbiology swab (MCS)		✓	✓		
Pain Assessment (NRS) (Appendix G)		✓	✓		
Pain and Scar Assessment (POSAS) (Appendix E, F)				✓	✓
Ultrasound of Transplanted Kidney (Study specific)				✓	✓
Adverse Event & Serious Adverse Event Assessment		✓	✓	✓	✓

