3.2 Secondary Objectives

Secondary objectives of this study include identification of risk factors for wound complications at the surgical site, as well as reoperation, prolonged hospital stay, allograft survival, delayed graft function. This study will also assess pain, scar healing and quality of life in each treatment arm, and aim to complete a cost-benefit analysis of the Prevena device in renal transplantation.

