4.2 Study Design

Ethics approval will be obtained from SLHD-RPA by the Lead site at RNSH. All sites will require Governance approval prior to study commencement. Enrolled participants in this study will present for renal transplantation at a participating study site, having received routine planning and workup for the operation which will include education regarding the trial, and providing informed consent at the time of admission for the operation. Study investigators will register the patient in an online database (REDCap Database Vanderbilt University) controlled by the study investigators, which will randomly allocate the patient to a treatment arm, to be revealed after transplantation and during the closure procedure (closure defined as closure to the muscle, subcutaneous tissue or skin). Patient data variables including demographic data, medical comorbidities and pathology results will be recorded from the patient electronic medical record (see appendix). Details of the donor kidney will be also be recorded, including donor demographics, anatomical characteristics, ischaemic time, and time of retrieval.

The patient will be prepared for surgery as per site specific protocols; variables to be recorded include peri operative antibiotic administration and skin preparation (application of an antiseptic agent such as chlorhexidine or iodine, or iodine impregnated drapes). Each surgeon will proceed with the procedure of renal transplantation as per operator preference. Operative details to be recorded include site and side of incision (Rutherford-Morrisson), warm ischaemic time, time of reperfusion, operation duration, estimated blood loss, length of incision, and method (materials; eg. sutures, staples) of closure in layers (muscle, subcutaneous tissue and skin). Drain presence and placement is also recorded. Bilateral renal transplants and bilateral incisions will be counted as one incision and will allocated to the same treatment arm as one entity.

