The perioperative recipient management will otherwise be identical in both the intervention and the control arms and guided by site specific protocols. Data will be recorded daily until the date of discharge regarding site specific practices in regard to immunosuppression, antibiotics, imaging, drain management, and pathology results. If the patient is discharged with a drain, volumes must be recorded till the date of removal. If the patient re-presents to hospital with a wound complication, requires a re-operation or subsequent interventions, this is recorded for the requisite primary and secondary endpoints by the study investigators.

All patients will follow up at time points below, for assessments of the surgical site and overall health (see appendix). The date of drain removal and volumes drained will be confirmed and recorded if the patient was discharged with a drain. On review, patients may also undergo an ultrasound, or other suitable imaging at investigator discretion, to determine the presence of deep wound complications. Imaging staff will be blinded to the patients allocated treatment arm in the trial.

The timeline for patient follow up and assessment is as follows:

Day 7 – The dressing is taken down for review and not replaced unless indicated. The review will include a microbiology swab (MCS), photo of the wound, modified ASEPSIS wound assessment, a pain assessment (NRS) and patient quality of life questionnaire (EQ-5D).

Day 14 – The dressing is taken down for review and not replaced unless indicated. The review will include a microbiology swab (MCS), photo of the wound, modified ASEPSIS wound assessment, a pain assessment (NRS), and quality of life questionnaire (EQ-5D).

Day 30 (+/- 3 days) – The patient will present for follow up for an extended wound review by a study clinician or wound CNC, and a vascular sonographer. The review will include a modified ASEPSIS wound assessment, a photo of the wound, a pain and scar assessment (POSAS), a quality of life questionnaire (EQ-5D), and an ultrasound of the transplanted kidney which will also identify deep wound complications.

90 days (+/- 3 days) – The patient will present for follow up for wound review and ultrasound, which will include a photo of the wound, a scar assessment (POSAS), a quality of life questionnaire (EQ-5D), and an ultrasound of the transplanted kidney which will also identify deep wound complications.

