4.6 Primary and Secondary Outcome Measures

Primary outcomes of this study include wound infection, wound dehiscence or fluid collection at the surgical site within 30 postoperative days (see Appendix for Classification of wound complications)

Secondary outcomes include pain, scar healing, quality of life, reoperation, duration and volume of wound drainage, graft function, hospital length of stay, clinical adverse events and mortality (see Appendix for NRS, POSAS, EQ 5D-5L and List of dependent variables).

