5. PARTICIPANT ENROLLMENT AND RANDOMISATION

5.1 Recruitment

All patients presenting for a renal transplant over a 24 month at one of the participating sites will be eligible for enrolment in this study. Only participants who give informed consent will be enrolled in the study, and this will be done by a study investigator. Participants may be recruited at any point after written informed consent, prior to surgery.

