9.3 Statistical Analysis Plan

Statistical analysis will be pre-specified and conducted according to both principles of intention to treat and per-protocol analysis, using SPSS version 20 (IBM, Armonk, NY, USA). Each incision will be randomized to the Prevena or standard dressing group. In the case that a patient requires bilateral incisions, both incisions will be allocated to the same treatment arm and counted as a single incision. Baseline characteristics of the two groups will be recorded and compared using Student's t-test and chi-square test for continuous and discrete data respectively. The primary outcome, the proportion of wound complications, will be compared between the Prevena and standard dressing groups using a chi-square test without Yates' continuity correction with a two-sided alpha of 0.05 at the final analysis using the Peto approach to preserve the overall significance level of 0.05 (23). An absolute risk increase/reduction for wound complications will be presented for the use of Prevena, as well as the number needed to treat in order to prevent specific wound complications. Patients lost to follow-up will be used in an intention-to-treat analysis with last observation carried forward.

The secondary outcome of identification of risk factors for wound complications will be assessed by multiple logistic regression of collected variables to assess their odds ratio. To prevent overfitting with the selected sample size, variables will be stepwise selected and also assessed for multicollinearity with the significance level of the dependent variables adjusted for multiplicity. Secondary outcomes will be compared between groups using a chi-square or Fisher's test for reoperation rate and delayed graft function and t-test for continuous variables, including the pain scale and quality of life. Non-normally distributed continuous variables will be tested for and compared using the Mann-Whitney *U* test. Survival analysis will be performed for allograft survival time with subjects without events censored at the 90 day final observation. A *p* value of less than 0.05 will be considered significant for the secondary outcomes and all tests will be two-sided.

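### EQ-5D-5L is first collected at Day 7, so the quality-of-life comparison cannot be adjusted for its baseline value and loses some precision

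*Combined protocol and SAP*

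**What the plan says.** Quality of life is a stated objective and a listed secondary outcome. Section 3.2: "This study will also assess pain, scar healing and quality of life in each treatment arm". Section 4.6: "Secondary outcomes include pain, scar healing, quality of life, reoperation".

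In the section 6 schedule, the row "Quality of life questionnaire (EQ-5D-5L) (Appendix D" is ticked at Days 7, 14, 30 and 90, and its Day 0 cell is empty. The visit narratives in sections 4.2 and 6 agree with the table. The first EQ-5D they mention is at Day 7, listed in section 4.2 as "a pain assessment (NRS) and patient quality of life questionnaire (EQ-5D".

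Day 0 carries only screening, consent and "Routine perioperative data collection (Appendix C". Section 4.2 describes the patient data as drawn from the record: "Patient data variables including demographic data, medical comorbidities and pathology results will be recorded from the patient electronic medical record". None of this is patient-reported health.

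The analysis in section 9.3 is a "t-test for continuous variables, including the pain scale and quality of life", with Mann-Whitney U for non-normal variables. No baseline covariate is named for quality of life.

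**The concern.** Some of the spread in post-operative EQ-5D-5L scores reflects how well each patient was before transplant. A pre-operative score lets the analysis remove that part of the variance from the comparison between arms. Without it, that part stays in the error term, and a chance imbalance in pre-transplant EQ-5D-5L can be neither seen nor adjusted for directly.

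The omission cannot be repaired at the analysis stage, because once the transplant has been done the pre-operative score is gone. What is at stake is the precision of one secondary outcome at each of its four time points.

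**Working it through.** **The plan's own figure.** The only sample size in the documents is for the primary outcome (section 9.1: 15% against 7%, two-sided alpha 0.05, power 80%). By the formula given there:

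n = {1.96 × √(0.11 × 0.89 × 2) + 0.84 × √(0.15 × 0.85 + 0.07 × 0.93)}² / 0.08² = 238.7, that is 239 per group.

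This matches the stated figure, and the present point does not touch it. The documents give no SD, target difference or power for EQ-5D-5L, so the rest is in SD units.

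**Inputs.**
- 250 per arm (section 9.1), allocated 1:1 (section 5.4).
- Two-sided 0.05 for secondary outcomes (section 9.3).
- Power of 80%, borrowed from the primary outcome as a yardstick.
- Correlation r between baseline and follow-up EQ-5D-5L: not in the documents, so assumed over 0.2 to 0.7.

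**Planned comparison, follow-up scores only.** Detectable difference = (1.960 + 0.842) × √(2/250) = 0.251 SD.

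**With baseline as a covariate (ANCOVA).** The variance is multiplied by 1 − r². The detectable difference is therefore 0.251 × √(1 − r²), and the effective size is 250/(1 − r²) per arm.

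| Assumed r | 1 − r² | Fall in SE | Detectable difference (SD) | Effective n per arm | Power at 0.25 SD |
|---|---|---|---|---|---|
| no baseline | 1.00 | – | 0.251 | 250 | 79.8% |
| 0.2 | 0.96 | 2.0% | 0.246 | 260 | 81.4% |
| 0.3 | 0.91 | 4.6% | 0.239 | 275 | 83.4% |
| 0.5 | 0.75 | 13.4% | 0.217 | 333 | 89.8% |
| 0.7 | 0.51 | 28.6% | 0.179 | 490 | 97.5% |

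**With a change score instead.** A t-test on change from baseline has variance 2(1 − r) relative to the raw score, if the SD is the same at both times. That is 1.6 at r = 0.2, 1.4 at 0.3, 1.0 at 0.5 and 0.6 at 0.7. Below r = 0.5 it is less precise than the comparison already planned. At every r in the table it is less precise than ANCOVA. The gain therefore comes from covariate adjustment, not from reporting change.

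**Is a baseline feasible?** Section 5.1 says "Participants may be recruited at any point after written informed consent, prior to surgery", and section 5.4 places randomisation after closure has begun. A form completed between consent and surgery always precedes allocation, so knowledge of the dressing cannot influence it.

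**The case against.** The strongest reply is that this is a choice and not an error. The schedule, the narratives and section 9.3 are consistent with one another: quality of life is measured after surgery and compared between randomised arms. No power target for it is stated, so none is missed. The correlation may well be low, since the baseline would precede a transplant and the follow-up falls 7 to 90 days after it. At r of 0.2 to 0.3 the standard error falls by only 2% to 5%. All of this stands, and it limits the weight of the point.

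A reader might infer three stronger things that the documents do not support:
- **That the comparison is biased.** It is not. Allocation is random and stratified by site, so a comparison of follow-up scores alone remains valid.
- **That nothing can be adjusted for.** Demographics, comorbidities and site are recorded and could be covariates. For those the obstacle is the choice of a t-test in section 9.3, not the empty Day 0 cell. Only the EQ-5D-5L value itself is out of reach.
- **That the cost-benefit objective is damaged.** Section 3.2 states an aim to complete such an analysis, but the documents do not say that it will use EQ-5D. A baseline score would be available to it if it does.

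Appendix C, which is ticked at Day 0, is not in the text available for review. It does not explain the blank cell, because EQ-5D-5L has its own row and its own appendix.

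The reply does not remove the loss of precision. That loss exists for any non-zero r and is cheap to avoid.

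**Conclusion.** The point holds as one of precision on a secondary outcome. Because EQ-5D-5L starts at Day 7, the quality-of-life comparison cannot be adjusted for its baseline. It stays unbiased, with a detectable difference of 0.251 SD where adjustment would give between 0.246 SD (r = 0.2) and 0.179 SD (r = 0.7). The gain is small at r of 0.3 or less and material at 0.5 or more.

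The figures assume 250 per arm with scores at the visit in question, a linear relation between baseline and follow-up, and the normal approximation. The range of r is an assumption, and nothing in the documents favours its upper end. The empty cell is certain, but its practical consequence is not. The primary endpoint, its sample size and the validity of the trial are unaffected.

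**What to change.** Two changes are needed, since neither is enough alone.

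1. In the section 6 schedule, and in the matching narrative in section 4.2, add EQ-5D-5L at Day 0, completed after consent and before surgery.
2. In section 9.3, replace the t-test for quality of life with ANCOVA at each time point, or a mixed model over Days 7, 14, 30 and 90. Use baseline EQ-5D-5L and site (the stratification factor) as covariates. Do not use a t-test on change scores. State how a missing baseline will be handled, so that patients without one stay in the comparison.

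The cost is one further completion at admission of an instrument the trial already uses. Some baseline forms will be missing in urgent cases. For patients already transplanted when the change is made, no baseline can be recovered.

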7. CLINICAL AND LABORATORY ASSESSMENTS

See Appendix C.

8. ADVERSE EVENT REPORTING

Adverse event reporting for clinical trials involving therapeutic products will meet the requirements of the National Health and Medical Research Council, Australian Health Ethics Committee (AHEC) Position Statement "*Monitoring and reporting of safety for clinical trials involving therapeutic products*" (May 2009), which can be found at:

www.nhmrc.gov.au/health_ethics/hrecs/reference/files/090609_nhmrc_position_statement.pdf

8.1 Definitions

Adverse event

An adverse event for medicines is also referred to as an adverse experience, any untoward medical occurrence in a patient or clinical investigation participant administered a pharmaceutical product and which does not necessarily have a causal relationship with this treatment. An adverse event can therefore be any unfavourable and unintended sign, symptom, or disease temporally associated with the use of a medicinal (investigational) product, whether or not related to the medicinal (investigational) product.

Devices Events

An adverse event for devices is any undesirable clinical occurrence in a participant whether it is considered to be device related or not, that includes a clinical sign, symptom or condition and/or an observation of an unintended technical performance or performance outcome of the device.

In relation to devices any adverse medical occurrences include: death and or a serious deterioration in health of a patient user or other. This would include:

- a life threatening illness or injury;
- a permanent impairment of body function or permanent damage to a body structure
- a condition requiring hospitalisation or increased length of existing hospitalisation
- a condition requiring unnecessary medical or surgical intervention or
- death or a serious deterioration in health had suitable action or intervention not taken place
- a malfunction of a device such that it has to be modified or temporarily/permanently taken out of service; or a factor (deterioration in characteristics or performance) found on examination of the device

8.2 Assessment and Documentation of Adverse Events

All adverse events (see Appendix C) will be documented in the study database.

8.3 Eliciting Adverse Event Information

Adverse events (see Appendix C) will be reviewed and confirmed at the follow up assessments.

8.3 Serious Adverse Event Reporting

8.3.1 SAEs

Serious adverse events will be recorded in the study data, and site-specific HREC reporting for incident and risk management will be followed.

Serious adverse event (SAE):

An unforeseen medical event that occurs in the course of clinical research that:

- results in participant death
- is life-threatening to the participant
- requires the inpatient hospitalisation or prolongation of existing hospitalisation and leads to the participant having a persistent or significant disability/incapacity.

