2. INTRODUCTION AND BACKGROUND

2.1 Background Information

Renal transplantation is considered to be the best treatment option for patients with end stage kidney disease in terms of quality of life and survival outcomes, as well as relative cost efficiency compared to dialysis.(1) Transplant recipients are susceptible to wound complications, arguably the most common post-transplant surgical complication, which may contribute to an additional risk of graft rejection or failure, prolonged length of stay, readmission and re-operation, as well as increased treatment costs. (2)

Wound complications have been previously superficial or deep dehiscence and/or infection, perigraft collections or seromas, cellulitis, lymphocoeles, and prolonged wound drainage. Studies have shown that the most important risk factors for wound complications in transplantation are immunosuppression and obesity (3). The incidence of wound infection in the presence of immunosuppression is approximately 7%, and more potent immunosuppressive agents are thought to result in a higher incidence of wound complications. (4) Comparing patients with high (>30) and low BMI (<30) patients, meta-analyses have demonstrated a significantly higher risk of wound infection (RR = 3.13, CI, 2.08–4.71; P <0.001), and wound dehiscence (RR 4.85, CI, 3.25–7.25; P <0.001). (5)(6)

Other relevant factors in renal transplantation include surgical technique and expertise, reoperative procedures, the presence of a haematoma, as well as recipient comorbidities such as advanced age, diabetes, malnutrition, dialysis (haemo- and peritoneal), and prolonged uraemia. The surgical closure technique of the incision, in particular, the precise closure of defects in each layer, has also been identified as an independent factor in reducing wound complications. (7) (8)

Negative pressure wound therapy (NPWT) utilises a foam sponge, in combination with a semipermeable adhesive dressing and a vacuum pump device to increase blood flow, drain fluid and exudate, and contract wound edges. Meta- analyses have suggested that when compared to standard wound dressings on closed incisions, NPWT significantly decreases wound size and healing time, with a significant reduction of risk of surgical site infections (RR=0.54, p= 0.01), and a significant reduction in risk of seroma formation (RR=0.48, p=0.01). (9) (10) (11).

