8.3.2 SUSARs

Suspected Unexpected Serious Adverse Reactions (SUSAR) will be recorded in the study data, and site-specific HREC reporting for incident and risk management will be followed.

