9.4 Interim Analyses

Interim review of recruitment will occur at the 6 month period, and interim analysis of preliminary data will occur at the 1 year mark. Sample size estimates will be reassessed given actual rates of enrolment after the 6 month period to ensure that the a priori sample size calculated is realistic, and the trial may be extended to allow for adequate patient recruitment. The trial will not be stopped for superiority reasons unless the adverse event rate and safety of the product is determined to be significant. Significance of the primary outcome will be assessed with an interim stopping level of $p=0.001$ using the Peto approach. (23)

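### Section 8.3.1 makes being unforeseen a condition of an SAE, so a serious event of a kind the protocol anticipates can miss the SAE label and its HREC reporting route

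*Combined protocol and SAP*

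**What the plan says.** All references are to the combined protocol and SAP.

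- **Section 8.3.1 (SAEs).** The definition opens "An unforeseen medical event that occurs in the course of clinical research that" and then lists three criteria: death, threat to life, and a combined criterion, "requires the inpatient hospitalisation or prolongation of existing hospitalisation and leads to the participant having a persistent or significant disability/incapacity". The consequence of the label is given in the same section: "Serious adverse events will be recorded in the study data, and site-specific HREC reporting for incident and risk management will be followed".
- **Section 8.1 (Definitions).** A device adverse event is "any undesirable clinical occurrence in a participant whether it is considered to be device related or not". The list that follows includes death, life-threatening illness or injury, and hospitalisation or a longer stay. It has no condition about foreseeability.
- **Section 8.3.2 (SUSARs).** Unexpectedness has its own category: "Suspected Unexpected Serious Adverse Reactions (SUSAR) will be recorded in the study data".
- **Section 2.1 (Background).** "Transplant recipients are susceptible to wound complications, arguably the most common post-transplant surgical complication". The same sentence links these complications to "additional risk of graft rejection or failure, prolonged length of stay, readmission and re-operation".
- **Section 4.6 and Appendix A.** Wound infection, dehiscence and fluid collection within 30 days form the primary outcome. Reoperation, graft function and mortality are among the secondary outcomes. Appendix A classifies the wound complications in eight classes.

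**The concern.** Seriousness and expectedness are different properties of an event. Seriousness describes how bad the outcome was. Expectedness describes whether that kind of event was anticipated. Section 8.3.1 makes the second a precondition of the first. In this trial the anticipated events are also the ones of most interest: infection and dehiscence at the incision, graft loss, reoperation and death. An investigator faced with a life-threatening deep wound infection could reasonably say that the protocol foresaw it and, on the wording, not class it as an SAE.

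What is at stake is the SAE label and the HREC route that 8.3.1 attaches to it. Consistency is also at stake. The word is not defined, and three sites must each interpret it. Section 5.4 leaves the surgical team and clinical staff unblinded, and section 5.5 says investigators can identify the treatment in the first 7 days and probably still at 14 days. The judgement could therefore differ between sites and, in principle, between arms.

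**Working it through.** The plan states no SAE count or rate, so there is no figure to reproduce. The check is a comparison of the definitions.

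**Step 1. Is the event anticipated by the protocol?** Wound complications, graft rejection or failure, readmission and reoperation are named in section 2.1. Wound events, reoperation, graft function and mortality are outcomes in section 4.6. The wound classes are set out in Appendix A, and section 9.1 assigns wound complications a rate of 15% in the control arm and 7% in the Prevena arm.

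**Step 2. Apply both definitions to the same event**, taking *unforeseen* to mean a kind of event that was not anticipated.

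| Event of an anticipated kind | Within the 8.1 device-event definition? | SAE under 8.3.1? | Reason |
|---|---|---|---|
| Fatal or life-threatening | Yes | No | Fails only on *unforeseen* |
| Hospitalised, with lasting disability | Yes | No | Fails only on *unforeseen* |
| Hospitalised or stay prolonged, without disability, not life-threatening | Yes | No | Fails on *unforeseen* and on the joined third criterion |

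The first two rows isolate the effect of the word. The third does not: such an event would fail even if *unforeseen* were deleted, because hospitalisation and disability are joined. That is a separate point about the same definition.

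**Step 3. Does another section restore the SAE label?** No section says that serious anticipated events are still SAEs, and none declares a deliberate exemption for endpoint events. Section 8.3.2 covers suspected reactions that are unexpected, so it does not catch anticipated ones.

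**Step 4. Are the events recorded elsewhere?** Yes.

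- Section 8.2 has every adverse event documented in the database, and the follow-up visits confirm them (section 8.3, on eliciting events).
- Section 6 schedules adverse event and SAE assessment at Days 7, 14, 30 and 90.
- Section 4.2 has wound-related re-presentations and reoperations recorded for the endpoints.

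**Step 5. Scale.** With 250 patients per arm and the rates in section 9.1, the expected number of patients with a wound complication is 250 × 0.15 + 250 × 0.07 = 37.5 + 17.5 = 55. This is the pool of anticipated wound events. It is not the number misclassified, because the documents do not give the share that is fatal, life-threatening or disabling.

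**The case against.** The strongest reply is that one loose word does little harm, because every event in question reaches the database by another route. On recording, that is right. A reader might infer from 8.3.1 that serious wound and graft events go unrecorded, and the sections in Step 4 contradict this.

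Three further inferences also fail.

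- **Stopping.** A reader might conclude that the interim safety judgement is undermined. Section 9.4 says "The trial will not be stopped for superiority reasons unless the adverse event rate and safety of the product is determined to be significant". It refers to adverse events, which under 8.1 carry no foreseeability condition, and not to SAE counts. An excess of wound complications would also show in the primary outcome, which has its own interim level of p = 0.001.
- **SAE comparison by arm.** The plan describes no such table, so the documents do not support a statement that it would omit most serious events.
- **A count of missed SAEs.** If 10% to 30% of the 55 were serious (an assumption), the result would be 5.5 to 16.5. Nothing in the documents supports that share. Appendix A includes cellulitis, superficial dehiscence, seroma and prolonged drainage, and some hospitalised cases would fail on the joined third criterion anyway.

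The word may also mean something narrower. Section 5.2.3 uses it for an intraoperative event, where it naturally means unplanned in that patient. On that reading an individual's life-threatening infection would be an SAE. The separate SUSAR category gives this some support, and SUSAR is not simply redundant, since it also requires a suspected causal link. Finally, section 8 promises to meet a national position statement on safety reporting, and 8.3.1 invokes site-specific HREC rules. Neither those requirements nor Appendix C, which sections 8.2 and 8.3 cite for adverse events, could be read here, so it cannot be shown that reports would actually be missed.

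These points soften the defect without removing it. The narrower meaning is possible but not stated, and a general commitment does not tell a site to set aside the explicit definition in front of it.

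**Conclusion.** The point holds as a defect of classification and reporting. Sections 8.1 and 8.3.1 disagree on whether an event must be unforeseen, and the stricter wording stands in the section that triggers HREC reporting. On the literal reading, fatal, life-threatening or disabling events of kinds the protocol anticipates can be left without the SAE label, and sites may differ in how they apply an undefined word.

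No number can be attached to this. The protocol's own rates imply about 55 patients with an anticipated type of wound complication, but how many would be serious is not given. The conclusion assumes that at least some investigators will read the word as referring to the kind of event, and that the external requirements cited in section 8 do not override the definition in practice. It does not rest on any loss of data or any effect on the primary analysis.

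**What to change.** In section 8.3.1, replace the opening words with: *Any adverse event (as defined in 8.1), whether or not expected or device related*, followed by the seriousness criteria. Use expectedness only in 8.3.2. If endpoint events are meant to be exempt from expedited reporting, say so explicitly and name the events, so that the exemption is a stated choice applied alike at all three sites.

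The cost is a one-line amendment, submitted to the HREC under section 11.2, and an expected/unexpected tick box on the case report form. The downside is small: more SAE entries, mostly for events already collected as outcomes.
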